Effective Date: 02Dec2019

## 1. INTRODUCTION

This document describes the rules and conventions to be used in the presentation and analysis of efficacy and safety data for Protocol 213152. It describes the data to be summarized and analyzed, including specifics of the statistical analyses to be performed.

This statistical analysis plan (SAP) is based on Protocol Amendment 02 dated 03-Mar-2022 and eCRF version 2.0 dated 10-Jun-2020.

## 2. STUDY OBJECTIVES AND ENDPOINTS

[figure not shown]
### 2.1. PRIMARY OBJECTIVE

The primary objective is to evaluate the anti-tumor activity per Response Evaluation Criteria in Solid Tumors (RECIST) 1.1 in participants with metastatic or locally advanced/unresectable urothelial cancer treated with bintrafusp alfa.

### 2.2. SECONDARY OBJECTIVE

The secondary objective is:

- Evaluate the safety and tolerability of bintrafusp alfa in participants with urothelial cancer

Document: [\\quintiles.net\Enterprise\Apps\sasdata\SAS\sas\GSK\GSK4045154\PZAA7715\Biostatistics\Documentation\SAP\GSK\\_213152\\_PZAA7715\\_SAP\\_Final\\_v1.0\\_07SEP2022](\\quintiles.net\Enterprise\Apps\sasdata\SAS\sas\GSK\GSK4045154\PZAA7715\Biostatistics\Documentation\SAP\GSK_213152_PZAA7715_SAP_Final_v1.0_07SEP2022)

Author: PPD Version Number: 1.0

Version Date: 07SEP2022

Template No.: CS\_TP\_BS016 Revision 6 Reference: CS\_WI\_BS005

Effective Date: 02Dec2019

CCI

C  
CI

## 2.4. ENDPOINTS

The primary, secondary and exploratory endpoints relevant to analyses to be performed based on this SAP are described in the following table:

Document: [\\quintiles.net\Enterprise\Apps\sasdata\SAS\sas\GSK\GSK4045154\PZAA7715\Biostatistics\Documentation\SAP\GSK\\_213152\\_PZAA7715\\_SAP\\_Final\\_v1.0\\_07SEP2022](\\quintiles.net\Enterprise\Apps\sasdata\SAS\sas\GSK\GSK4045154\PZAA7715\Biostatistics\Documentation\SAP\GSK_213152_PZAA7715_SAP_Final_v1.0_07SEP2022)

Author: PPD Version Number: 1.0

Version Date: 07SEP2022

Template No.: CS\_TP\_BS016 Revision 6

Reference: CS\_WI\_BS005

Effective Date: 02Dec2019

Table A: List of Endpoints

Objectives	Endpoints	SAP Section	Analysis Set	Variable
Primary				
Evaluate the anti-tumor activity per RECIST 1.1 in participants with metastatic or locally advanced/unresectable urothelial cancer treated with bintralusp alfa	Confirmed Overall Response per RECIST 1.1 assessed by investigator.	13.1	Safety/Treated	ORR (by Investigator)
Secondary				
Evaluate the safety and tolerability of bintralusp alfa in participants with urothelial cancer.	Frequency and severity of AEs using Error! Reference source not found..	14.1.1	Safety/Treated	Treatment Emergent Adverse Events (TEAE)

Document: [\\quintiles.net\Enterprise\Apps\sasdata\SAS\sas\GSK\GSK4045154\PZAA7715\Biostatistics\Documentation\SAP\GSK\\_213152\\_PZAA7715\\_SAP\\_Final\\_v1.0\\_07SEP2022](\\quintiles.net\Enterprise\Apps\sasdata\SAS\sas\GSK\GSK4045154\PZAA7715\Biostatistics\Documentation\SAP\GSK_213152_PZAA7715_SAP_Final_v1.0_07SEP2022)

Author: PPD Version Number: 1.0

Version Date: 07SEP2022

Template No.: CS\_TP\_BS016 Revision 6

Reference: CS\_WI\_BS005

Effective Date: 02Dec2019

Objectives	Endpoints	SAP Section	Analysis Set	Variable
CCI				
CCI				
CCI				

CCR = Best Overall Response; NCI CTCAE = Toxicity Grading based on national Cancer Institute-Common Terminology Criteria for Adverse Events v5; ORR = overall response rate; CCI  
CCR; RECIST 1.1 = Response Evaluation Criteria in Solid Tumors Version 1.1.

### 3. STUDY DESIGN

#### 3.1. GENERAL DESCRIPTION

This is a Phase Ib open-label, global, multicenter, single-arm trial of bintralusp alfa administered to participants with metastatic or locally advanced/unresectable urothelial cancer with disease progression or recurrence following treatment with a platinum agent.

The primary study objective is to evaluate the ORR per RECIST v1.1. The secondary objective is to evaluate safety and tolerability of bintralusp alfa.

Participants who permanently discontinue study treatment will enter the follow-up period of the study and undergo the assessments as indicated in Section 8 of the Protocol.

Approximately 25 participants will be treated in this study.

The study includes:

- 45-day screening period
- Treatment with bintralusp alfa 1200 mg as an IV infusion Q2W until disease progression

Document: [\\quintiles.net\\Enterprise\\Apps\\sasdata\\SAS\\sas\\GSK\\GSK4045154\\PZAA7715\\Biostatistics\\Documentation\\SAP\\GSK\\_213152\\_PZAA7715\\_SAP\\_Final\\_v1.0\\_07SEP2022](\\quintiles.net\\Enterprise\\Apps\\sasdata\\SAS\\sas\\GSK\\GSK4045154\\PZAA7715\\Biostatistics\\Documentation\\SAP\\GSK_213152_PZAA7715_SAP_Final_v1.0_07SEP2022)

Author: PPD Version Number: 1.0

Version Date: 07SEP2022

Template No.: CS\_TP\_BS016 Revision 6

Reference: CS\_WI\_BS005

Effective Date: 02Dec2019

as determined by Investigator using RECIST v1.1 (Eisenhauer EA, 2009) death, unacceptable toxicity, study withdrawal, or up to 2 years (see Protocol, Section 7).

- Participants who have experienced a confirmed complete response (CR) can continue treatment for a maximum of 24 months after confirmation of response (at the discretion of the Investigator). If the Investigator believes that a participant with confirmed CR may benefit from treatment beyond 24 months, it may be permissible to continue treatment after discussion with the GSK Medical Monitor.
- Participants with stable disease (SD) or partial response (PR) should continue treatment up to a period of 24 months from first dose until disease progression, or any other discontinuation criterion is met.
- Safety Follow-up: will continue until 12 weeks after the last administration of bintralusp alfa. The 12-week Safety Follow-up can be conducted via telephone calls or participant chart reviews unless there is medical necessity requiring a clinical visit.
- Long-term Follow-up: should be performed every 12 weeks after the Safety Follow-up according to the Schedule of Activities (see Section 1.3 of the Protocol). Long-term Follow-up should be performed by chart reviews or telephone calls.
- Once the Data Cut-Off (DCO) date for the final analysis for this study has been reached, the clinical study database will be closed to new data and any participants that continue to receive study intervention at this time will be followed as described in Section 8.2 of the protocol.

Biopsies prior to study treatment are required, as described in eligibility criteria (see Protocol Section 5.1). CC1

CC1

Document: [\\quintiles.net\Enterprise\Apps\sasdata\SAS\sas\GSK\GSK4045154\PZAA7715\Biostatistics\Documentation\SAP\GSK\\_213152\\_PZAA7715\\_SAP\\_Final\\_v1.0\\_07SEP2022](\\quintiles.net\Enterprise\Apps\sasdata\SAS\sas\GSK\GSK4045154\PZAA7715\Biostatistics\Documentation\SAP\GSK_213152_PZAA7715_SAP_Final_v1.0_07SEP2022)

Author: PPD Version Number: 1.0

[figure not shown]
Version Date: 07SEP2022

Template No.: CS\_TP\_BS016 Revision 6

Reference: CS\_WI\_BS005

Effective Date: 02Dec2019

Table B: STUDY SCHEMA

### 3.2. SCHEDULE OF ACTIVITIES

Schedule of activities can be found in Section 1.3 of the Protocol.

### 3.3. CHANGES TO ANALYSIS FROM PROTOCOL

- The term “AEs” in the endpoint “Frequency and severity of AEs” associated with the secondary objective “Evaluate the safety and tolerability of bintralusp alfa in participants with urothelial cancer” in the protocol, refers to adverse events that begin on or after the start of the study treatment or worsened after the start of the study treatment and therefore are treatment-emergent AEs (TEAEs). TEAEs will be used as the endpoint to be reported in this SAP.
- Due to special circumstances relating to the COVID-19 pandemic, the specific guidance from local public health and other competent authorities regarding the protection of individuals’ welfare will be applied. For the duration of such special circumstances, the

Document: [\\quintiles.net\Enterprise\Apps\sasdata\SAS\sas\GSK\GSK4045154\PZAA7715\Biostatistics\Documentation\SAP\GSK\\_213152\\_PZAA7715\\_SAP\\_Final\\_v1.0\\_07SEP2022](\\quintiles.net\Enterprise\Apps\sasdata\SAS\sas\GSK\GSK4045154\PZAA7715\Biostatistics\Documentation\SAP\GSK_213152_PZAA7715_SAP_Final_v1.0_07SEP2022)

Author: PPD Version Number: 1.0

Version Date: 07SEP2022

Template No.: CS\_TP\_BS016 Revision 6

Reference: CS\_WI\_BS005

Effective Date: 02Dec2019

following may impact the data and analysis:

- Delayed FPI (First Patient In)
- Protocol deviations due to COVID-19
- Missed visits due to COVID-19
- Missed or modified assessments
- Treatment interruptions or delays
- Early study discontinuation or withdrawals due to having COVID-19 or COVID-19 related issues
- Adverse events or SAEs due to COVID-19.

## 4. PLANNED ANALYSES

All planned analyses identified in this SAP will be performed in a Final Analysis by IQVIA Biostatistics following Sponsor Authorization of this Statistical Analysis Plan and Database Lock.

## 5. ANALYSIS SETS

Definitions for analysis sets are provided below.

CCI

### 5.1. SCREENED ANALYSIS [SCR] SET

The Screened Analysis (SCR) set will contain all participants who sign the ICF.

### 5.2. SAFETY/TREATED ANALYSIS SET [SAF]

The safety/treated analysis set (SAF) will contain all participants who were administered at least one infusion of bintrafusp alfa.

If there is any doubt whether a participant was treated or not, they will be assumed to have

Document: [\\quintiles.net\Enterprise\Apps\sasdata\SAS\sas\GSK\GSK4045154\PZAA7715\Biostatistics\Documentation\SAP\GSK\\_213152\\_PZAA7715\\_SAP\\_Final\\_v1.0\\_07SEP2022](\\quintiles.net\Enterprise\Apps\sasdata\SAS\sas\GSK\GSK4045154\PZAA7715\Biostatistics\Documentation\SAP\GSK_213152_PZAA7715_SAP_Final_v1.0_07SEP2022)

Author: PPD Version Number: 1.0

Version Date: 07SEP2022

Template No.: CS\_TP\_BS016 Revision 6

Reference: CS\_WI\_BS005

Effective Date: 02Dec2019

been treated for the purposes of analysis. This is the primary analysis set for reporting efficacy and safety.

## 6. GENERAL CONSIDERATIONS

### 6.1. REFERENCE START DATE AND STUDY DAY

Study Day will be calculated from the reference start date and will be used to show start/stop day of assessments and events.

Reference start date is defined as the day of the first administration of study treatment (Day 1 is the day of the first administration of study treatment).

- If the date of the event is on or after the reference date, then:

Study Day = (date of event – reference date) + 1.

- If the date of the event is prior to the reference date, then:

Study Day = (date of event – reference date).

In the situation where the event date is partial or missing, the date will appear partial or missing in the listings, and Study Day, and any corresponding durations will be presented based on the imputations specified in Appendix 2; Partial Date Conventions.

### 6.2. BASELINE

Unless otherwise specified, baseline is defined as the last available/non-missing measurement taken prior to reference start date.

- If an assessment is planned to be performed prior to the first administration of study treatment in the protocol and the assessment is performed on the same day as the first administration of study treatment, it will be assumed that it was performed prior to study treatment, if assessment time is not collected or is missing.
- If assessment time is collected, the observed time as well as time of first dose of study

Document: [\\quintiles.net\Enterprise\Apps\sasdata\SAS\sas\GSK\GSK4045154\PZAA7715\Biostatistics\Documentation\SAP\GSK\\_213152\\_PZAA7715\\_SAP\\_Final\\_v1.0\\_07SEP2022](\\quintiles.net\Enterprise\Apps\sasdata\SAS\sas\GSK\GSK4045154\PZAA7715\Biostatistics\Documentation\SAP\GSK_213152_PZAA7715_SAP_Final_v1.0_07SEP2022)

Author: PPD Version Number: 1.0  
Version Date: 07SEP2022

Template No.: CS\_TP\_BS016 Revision 6 Reference: CS\_WI\_BS005

Effective Date: 02Dec2019

treatment will be used to determine pre-dose on study day 1 for baseline calculation.

- Unscheduled assessments will be used in the determination of baseline. However, if time is missing, an unscheduled assessment on Study Day 1 will be considered to have been obtained after study treatment.

In the case where the last non-missing measurement and the reference start date coincide, that measurement will be considered pre-baseline, but Adverse Events (AEs) and medications commencing on the reference start date will be considered post-baseline.

## 6.3. DERIVED TIMEPOINTS

### 6.3.1. ON-TREATMENT PERIOD

The on-treatment period is defined as the time from first study treatment to the last study treatment date plus 30 days or the earliest date of subsequent anticancer therapy minus 1 day, whichever occurs first, unless otherwise stated.

For participants with treatment ongoing at cut-off date, all data from the first study treatment up to the cut-off date will be considered under the on-treatment period.

Any systemic anticancer therapy, any anticancer surgery and any anticancer radiotherapy as documented in the "Anti-cancer treatment after discontinuation" eCRF page will be considered as subsequent anticancer therapy.

In the case of treatment delay, the definition for on-treatment period remains the same.

## 6.4. RETESTS, UNSCHEDULED VISITS AND EARLY TERMINATION DATA

For efficacy analyses, unscheduled assessments can be used in the determination of baseline according to Section 6.2. Unscheduled visits post-baseline will be excluded from table summaries CCI but will be included in listings.

Document: [\\quintiles.net\Enterprise\Apps\sasdata\SAS\sas\GSK\GSK4045154\PZAA7715\Biostatistics\Documentation\SAP\GSK\\_213152\\_PZAA7715\\_SAP\\_Final\\_v1.0\\_07SEP2022](\\quintiles.net\Enterprise\Apps\sasdata\SAS\sas\GSK\GSK4045154\PZAA7715\Biostatistics\Documentation\SAP\GSK_213152_PZAA7715_SAP_Final_v1.0_07SEP2022)

Author: PPD  Version Number: 1.0

Version Date: 07SEP2022

Template No.: CS\_TP\_BS016 Revision 6 Reference: CS\_WI\_BS005

Effective Date: 02Dec2019

Listings will include scheduled, unscheduled, retest and early discontinuation data.

Re-screened participants will only be counted once in the SCR, and will consider only the latest screening (screening with the latest informed consent).

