Bintrafusp alfa administration		X	X	X	X	X	X	X	Q2W				Bintrafusp alfa is administered as a 1200 mg IV infusion over 1 hour (-10 minutes/+20 minutes; ie, over 50 to 80 minutes) Q2W for up to 2 years (or up to 2 years from confirmed CR). See Section 6.1 for information.	

	Screening	Intervention (treatment) Period								Safety Follow-up		Long Term Follow-up	Notes	
Assessment and Procedures	45 Day- to first dose	V1	V2	V3	V4	V5	V6	V7	Until PD	EOT	28 Days (±5 Days) After Last Treatment	12 Weeks (± 2 Weeks) After Last Treatment	Every 12 Weeks (± 2 Weeks)	D1: All assessments must be performed on day indicated (unless noted in assessment "Notes"). Day 15 through PD: Visits can be performed ±3 days. EOT: On day of or within 7 days of decision to discontinue. Follow up: Visits can be performed ±2 Weeks.
		W1	W3	W5	W7	W9	W11	W13						
		D1	D15	D29	D43	D57	D71	D85						
Response Assessments														
Tumor evaluation/staging (CT Scan/MRI/ other established methods)	X					X			Q8W up to 6 months., then Q12W	X	X		CT scan with contrast of the chest, abdomen, and pelvis is required. Screening scans for lesion assessments are required within 28 days of first dose. See Section 8.3 for additional information Q8W for the first 6 months (mos.) and Q12W thereafter, and at the final study visit. Schedule should not be affected by dose interruptions/delays. Confirmation of CR and/or PR should be performed at the next scheduled assessment but no sooner than 4 weeks. Before stopping the treatment, progressive disease should be confirmed by imaging at least 4 weeks after progression. See Section 7.1.1. If discontinued intervention without documented progression, then continue imaging Q8W for the first 6 months followed by Q12W until documented PD, or the start of any new anti-cancer therapy. A bone scan should be done as clinically indicated at screening and beyond. TA brain CT/MRI scan should be performed as clinically indicated	

	Screening	Intervention (treatment) Period								Safety Follow-up		Long Term Follow-up	Notes				
Assessment and Procedures	45 Day- to first dose	V1	V2	V3	V4	V5	V6	V7	Until PD	EOT	28 Days (\pm 5 Days) After Last Treatment	12 Weeks (\pm 2 Weeks) After Last Treatment	Every 12 Weeks (\pm 2 Weeks)	D1: All assessments must be performed on day indicated (unless noted in assessment "Notes"). Day 15 through PD: Visits can be performed \pm 3 days. EOT: On day of or within 7 days of decision to discontinue. Follow up: Visits can be performed \pm 2 Weeks.			

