8.3. Evaluation of Anti-Cancer Activity

RECIST version 1.1 guidelines will be used to determine the overall tumor burden at baseline, select target and non-target lesions, and in the disease assessments throughout the duration of the study. The primary measure of response-based efficacy endpoints is according to RECIST v1.1 definition as assessed by the investigator [Eisenhauer, 2009].

- Response assessments will be performed Q8W for the first 6 months and Q12W thereafter, until end of treatment, and at the final study visit (refer to [Table 1](#)).
- If bintrafusp alfa is discontinued without documented progression, then continue imaging Q8W for the first 6 months from first dose of bintrafusp alfa followed by Q12W until documented PD, or the start of any new anti-cancer therapy.
- For post-baseline assessments, a window of [± 3 days] is permitted to allow for flexible scheduling.

Assessments must be performed on a calendar schedule and should not be affected by dose interruptions/delays.

If the last radiographic assessment was 6 weeks or more prior to the participant's withdrawal from study treatment and PD has not been documented, a disease assessment should be obtained at the time of withdrawal from study treatment. See [Table 1](#) for the schedule of assessments of anti-cancer activity.

- All the scans performed during screening need to be repeated at subsequent visits for tumor assessment.
- To ensure comparability between the baseline and subsequent assessments, the same method of assessment and the same technique must be used when assessing response.

Refer to the imaging manual for details on imaging/clinical assessment requirements and submission guidelines.

Tumor responses to treatment will be assigned based on the evaluation of the response of target, non-target, and new lesions according to RECIST v1.1.

Treatment decisions will be made by the treating investigator based on RECIST v1.1. Study intervention should continue until disease progression, unacceptable toxicity, or any criterion for withdrawal from the trial or study intervention occurs (see Section [7](#)). Before stopping the treatment, progressive disease should be confirmed by imaging at least 4 weeks after initial progression according to RECIST v1.1.

See Section 7.1 for more information about continued study intervention after disease progression.

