SRM/imaging manual), MRI, is required at each post-baseline assessment. To ensure comparability between the baseline and subsequent assessments, the same method of assessment and the same technique will be used when assessing response.

Refer to [Table 1](#) for the frequency of disease assessment. Assessments must be performed on a calendar schedule and should not be affected by dose interruptions/delays.

Participants whose disease responds (either CR or PR) should have a confirmatory disease assessment performed at least 4 weeks after the date of assessment during which the response was demonstrated. More frequent disease assessments may be performed at the discretion of the investigator.

If study treatment is resumed upon disease progression and following consultation with the investigator and GSK medical monitor, imaging scans which indicated progression will serve as the baseline scans. Representative new lesions, if measurable, may be incorporated into the evaluation of disease burden.

The foreseen treatment duration is until disease progression verified by a scan subsequent to the initial documentation of PD, unacceptable toxicity, or any criterion for withdrawal from the trial or study intervention occurs (see Section [7.1.1](#)).

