## 6.5. WINDOWING CONVENTIONS

No visit windowing will be performed for this study.

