#### 13.1.1. PRIMARY EFFICACY VARIABLE(S) & DERIVATION(S)

The primary efficacy endpoint is the confirmed objective response by the investigator. Overall response rate (ORR) is defined as the percentage (%) of participants with a best overall response (BOR) of PR or CR as assessed by the investigator using RECIST 1.1 out of the total number of participants in the SAF. Tumor response i.e., complete response (CR), partial response (PR), and stable disease (SD), and progressive disease (PD) will be based on the assessments from the investigators' assessment of objective evidence (e.g., radiological scan). Overall responses will be measured in accordance with the RECIST v1.1 (Eisenhauer EA, 2009).

Lesion assessment method and timing, evaluation of disease, disease progression and response criteria will be conducted according to RECIST (version 1.1) as outlined in Section 8.3 of the protocol. If there are multiple scan dates associated with an evaluation, the earliest of the scan dates associated with the evaluation will be used as the date of assessment.

Best overall response (BOR) will be assessed based on the tumor response determined by the investigator at each evaluation timepoint from the first study treatment until the first documented disease progression for RECIST criteria. Only tumor assessments performed before the start of any further anticancer treatment will be considered in the assessment of

Document: [\\quintiles.net\Enterprise\Apps\sasdata\SAS\sas\GSK\GSK4045154\PZAA7715\Biostatistics\Documentation\SAP\GSK\\_213152\\_PZAA7715\\_SAP\\_Final\\_v1.0\\_07SEP2022](\\quintiles.net\Enterprise\Apps\sasdata\SAS\sas\GSK\GSK4045154\PZAA7715\Biostatistics\Documentation\SAP\GSK_213152_PZAA7715_SAP_Final_v1.0_07SEP2022)

Author: PPD Version Number: 1.0

Version Date: 07SEP2022

Template No.: CS\_TP\_BS016 Revision 6

Reference: CS\_WI\_BS005

Effective Date: 02Dec2019

BOR. Clinical deterioration will not be considered as documented disease progression.

Confirmed BOR according to RECIST 1.1 (Eisenhauer EA, 2009) will be assessed according to the following rules:

- CR = at least two determinations of CR at least 4 weeks apart and before progression.
  - Note: It is reasonable to consider CR-NE-CR or CR-PR-CR as CR as long as the second CR is more than 28 days away from the first timepoint.
- PR = at least two determinations of PR at least 4 weeks apart and before progression (and not qualifying for a CR)

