### 13.1.3. FINAL ANALYSIS OF PRIMARY EFFICACY VARIABLE(S)

Confirmed BOR will be summarized as the number and percentage of participants with confirmed CR, PR, SD, PD or NE. In addition, the number of participants achieving objective response will be summarized. The corresponding two-sided 95% Confidence Interval (CI) for ORR will be calculated using the Clopper-Pearson (exact) method (Clopper C, 1934) with exact CI for binomial proportion as computed by default by the FREQ procedure using the EXACT option. There will be no adjustments for multiplicity.

Document: [\\quintiles.net\Enterprise\Apps\sasdata\SAS\sas\GSK\GSK4045154\PZAA7715\Biostatistics\Documentation\SAP\GSK\\_213152\\_PZAA7715\\_SAP\\_Final\\_v1.0\\_07SEP2022](\\quintiles.net\Enterprise\Apps\sasdata\SAS\sas\GSK\GSK4045154\PZAA7715\Biostatistics\Documentation\SAP\GSK_213152_PZAA7715_SAP_Final_v1.0_07SEP2022)

Author: PPD Version Number: 1.0

Version Date: 07SEP2022

Template No.: CS\_TP\_BS016 Revision 6

Reference: CS\_WI\_BS005

Effective Date: 02Dec2019

- The following reasons for non-evaluable confirmed best overall response will also be included in the summary:
  - No baseline assessment (if applicable)
  - No post-baseline assessments due to death within 8 weeks after the start of study treatment
  - No post-baseline assessments due to other reasons
  - All post-baseline assessments have overall response “Non-evaluable”
  - New anticancer therapy started before first evaluable post-baseline assessment
  - SD of insufficient duration (<6 weeks after the start of study treatment)
  - No evaluable tumor assessment >16 weeks followed by PD (i.e. tumor assessment of PD was >16 weeks after start of study treatment and there was no evaluable tumor assessment in between)
  - Not determined category may also be added if applicable.

CCI

Document: [\\quintiles.net\Enterprise\Apps\sasdata\SA\SAsas\GSK\GSK4045154\PZAA7715\Biostatistics\Documentation\SAP\GSK\\_213152\\_PZAA7715\\_SAP\\_Final\\_v1.0\\_07SEP2022](\\quintiles.net\Enterprise\Apps\sasdata\SA\SAsas\GSK\GSK4045154\PZAA7715\Biostatistics\Documentation\SAP\GSK_213152_PZAA7715_SAP_Final_v1.0_07SEP2022)

Author: PPD Version Number: 1.0

Version Date: 07SEP2022

Template No.: CS\_TP\_BS016 Revision 6 Reference: CS\_WI\_BS005

Effective Date: 02Dec2019

CCI

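### Does the SAP's exclusion of unscheduled visits from table summaries take off-schedule scans out of the primary ORR?

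*SAP*

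**What the plan says.** SAP 6.4 opens its paragraph with efficacy analyses and lets unscheduled assessments serve as baseline. It then states: "Unscheduled visits post-baseline will be excluded from table summaries". A redaction follows directly, and the sentence ends by keeping such visits in listings. SAP 6.5 adds: "No visit windowing will be performed for this study".

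SAP 13.1.1 derives BOR from the tumor response determined by the "investigator at each evaluation timepoint from the first study treatment until the first" documented progression. The confirmation rule reads "PR = at least two determinations of PR at least 4 weeks apart and before progression", and CR has a parallel rule. The section gives two limits: scans after the start of further anticancer treatment do not count, and clinical deterioration is not documented progression. For the method and timing of lesion assessment it refers to protocol 8.3.

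SAP 13.1.3 describes the primary table: "Confirmed BOR will be summarized as the number and percentage of participants with confirmed CR, PR, SD, PD or NE". It adds the ORR with an exact 95% interval.

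Protocol 8.3 sets scans every 8 weeks for 6 months and every 12 weeks after that. Protocol 8.3.1.1 adds: "More frequent disease assessments may be performed at the discretion of the investigator". On confirmation, the Schedule of Activities says: "Confirmation of CR and/or PR should be performed at the next scheduled assessment but no sooner than 4 weeks". If treatment stops without progression and the last scan is at least 6 weeks old, protocol 8.3 says "a disease assessment should be obtained at the time of withdrawal from study treatment".

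**The concern.** The primary endpoint is tabulated in a summary, and 6.4 appears to keep unscheduled post-baseline data out of summaries for efficacy analyses. Sections 6.4 and 13.1.1 do not cite each other, and without windowing an extra scan cannot be assigned to a planned visit. A programmer who applied 6.4 first and 13.1.1 second would derive BOR from planned scans only.

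That could change responder status in either direction. A response is lost if one of its only two qualifying scans was off schedule. A response is gained if an off-schedule first progression is ignored and two PRs at least 4 weeks apart then appear to stand without progression between or before them. With 25 participants and one proportion as the primary result, a single reclassification is visible.

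**Working it through.** The plan states no figure that is in dispute, so there is none to reproduce. The check has three parts.

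**1. Can the reading change a participant's status?**

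Rules from SAP 13.1.1: PR is two PRs at least 4 weeks apart before first PD; SD is SD or better at 6 weeks or later; PD is progression by week 16; otherwise NE. Assume one unscheduled scan at week 12 (PR, SD, PD or NE) between planned scans (PR, SD, PD, NE or absent).

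| Week 8 | Week 12 (unscheduled) | Week 16 | Week 24 | All scans | Planned scans only |
|---|---|---|---|---|---|
| PR | PR | PD | – | PR | SD |
| SD | PR | PR | PD | PR | SD |
| PR | PD | PR | – | SD | PR |

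With planned scans at weeks 8 and 16 there are 5 × 4 × 5 = 100 patterns.
- Lost: PR-PR followed by SD, PD, NE or absent (4), and SD, NE or absent followed by PR-PR (3), so 7.
- Gained: PR-PD-PR, so 1.

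With week 24 added there are 5 × 4 × 5 × 5 = 500 patterns.
- Lost: 38. Starting with PR, 25 − 8 = 17. Starting with SD, NE or absent, 3 × (8 − 1) = 21.
- Gained: 11. Starting with PR, 8. Starting with SD, NE or absent, 3 × 1 = 3.

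These count possible patterns. They are not probabilities, because every pattern is given an extra scan by construction.

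**2. How large is one change?**

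N = 25 (protocol 9.2). One participant is 1/25 = 4.0 percentage points. The Clopper-Pearson limits for x responders are the 2.5% quantile of Beta(x, 25 − x + 1) and the 97.5% quantile of Beta(x + 1, 25 − x). For assumed counts:
- 4/25 = 16.0% (4.5 to 36.1)
- 5/25 = 20.0% (6.8 to 40.7)

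The two intervals overlap over most of their length.

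**3. Does the SAP call for planned scans only?**

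- *What each rule governs.* Section 6.4 keeps unscheduled visits out of tables. BOR is one derived value per participant, and the 13.1.3 table counts participants. The visible text of 6.4 does not say that data are removed before a derivation.
- *Which scans enter.* Section 13.1.1 uses each evaluation timepoint up to first documented PD, and neither of its two limits is about scheduling. For timing it points to protocol 8.3, whose subsection 8.3.1.1 permits the extra scans.
- *Units.* The rules run on elapsed time (4 weeks, 28 days, 6 weeks, 16 weeks) and not on visit names, so the absence of windowing does no harm.
- *Reasons for NE.* Section 13.1.3 refers to post-baseline assessments without restricting them to planned ones, and gives no reason for a participant whose only evaluable scan was unscheduled. It does include SD seen before 6 weeks. The first planned scan is on Day 57 (Table 1), 56 days after first dose. With the ±3 days of protocol 8.3 that is 53 to 59 days, against 6 × 7 = 42. Only an extra or end-of-treatment scan can fill that category, so the section did not assume planned scans alone.
- *Conflict test.* Ignoring an off-schedule PD, as in the third row above, would carry BOR past the first documented progression, which 13.1.1 forbids.

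**The case for a change.** The best argument for a change is the SAP's own vocabulary. Section 6.6 uses table summaries for categorical tables in general and then treats by-visit summaries separately, so 6.4 is not plainly confined to by-visit tables. Laboratory, ECG and vital-sign data are described as listings, which leaves the BOR and ORR table as the only visible efficacy table the exclusion could reach. Two programmers could differ, and the tumor listing, which keeps unscheduled scans, could then disagree with the table. One sentence would prevent this.

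Part of that stands: the visible text has no cross-reference, and 6.4 is worded more broadly than it needs to be. The argument from the only visible table is weak, however. Most of the efficacy section after 13.1.3 is redacted, and SAP 7.3 cites a Section 13.2.3 that cannot be seen, so 6.4 may be aimed at tables that are hidden. The redaction inside the 6.4 sentence may hold a qualifier or only another type of output; neither can be shown. The remaining ambiguity lies between a general presentation convention and a specific derivation rule, and ordinary practice follows the specific rule.

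**Conclusion.** No change follows. Section 13.1.1, applied as written, counts scheduled and unscheduled scans alike toward response, confirmation and first progression, and gives a sound ORR. The feared error needs an extra step that the visible 6.4 does not contain and that 13.1.1 excludes where the scan shows progression.

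The potential effect is 4.0 percentage points per affected participant. The number affected is unknown and may be zero. The Schedule of Activities places confirmation at the next planned scan, withdrawal scans are specified by the protocol, and a scan that only confirms a recorded PD leaves BOR unchanged. No visible decision rule depends on the result, since the ORR is estimated with an interval. A cross-reference between 6.4 and 13.1.1 would be harmless tidying.

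This rests on two assumptions: that the redacted words in 6.4 do not extend the exclusion to derivations, and that analysts treat 13.1.1 as the governing rule for the primary endpoint.
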